#### *End of Study (EOS) Period*

The EOS period was on Day 21 (+3 days). The subjects visited the clinic on this day for the assessments such as vital signs, blood examinations (hematology, chemistry, and inflammatory blood examinations), photograph of the area of application, visual assessment of the area of application, AEs, and concomitant medications used.

The assessments at this visit were also to be conducted in case of early termination or withdrawal of any subject.

### Study Participants

Subjects were eligible to be included in the study only if they met all the following criteria:

1. Signed ICF prior to entering the study or undergoing any study procedures.
2. Male or female, >21 years of age at the time of signing the informed consent.
3. Subject who had been fully vaccinated for COVID-19 and was not under quarantine or Stay Home Notice or on a medical leave.
4. Subject who was willing and able to comply with scheduled visits, treatment plan, laboratory tests, and other study procedures.
5. Subject was able to read and write in the English language.
6. For women who were not postmenopausal (> 12 months of non-therapy induced amenorrhea) or surgically sterile (absence of ovaries and/or uterus):
  - a. had a negative pregnancy test at screening
  - b. remained abstinent or used contraceptive methods during the treatment period and continued for at least 30 days (one menstrual cycle) after the last treatment dose.

Subjects were to be excluded from the study if there was evidence of any of the following at screening or check-in, as appropriate:

1. Subject had any serious skin condition that was not well controlled.
2. Subject was currently using topical treatments.

3. Pregnant or breast-feeding women.
4. Subject had received phototherapy, oral corticosteroids, oral retinoid, oral immunosuppressive / immune modulatory drugs, cytostatic / cytotoxic drugs, cyclosporine, or methotrexate within 30 days prior to the first application of the study product.
5. Subject was currently using any medications including biologics or undergoing treatment known to affect skin conditions.
6. Subject had any other clinically significant laboratory abnormalities, co-morbidities or psychiatric conditions that would place the subject at increased risk or confound the objectives of the study.
7. Subject had used any investigational drugs or biologics and/or participated in any clinical trial within the last 60 days before the day of the first dose of the study drug or was taking part in a non-medication study that would interfere with study compliance or outcome assessments.

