Before the conduct of this study, PTD 2021P has not been administered to humans thus far. Therefore, this phase 1 study was the first to evaluate the safety and tolerability of the application of the MSC exosome ointment with repeated topical application on adult healthy subjects (TID from Day 1 to 20). The results of this study were to provide the first clinical information on the drug's safety and inform the selection of administration of exosome ointment to be evaluated in subsequent clinical studies. The endpoints included to assess the safety and tolerability of exosome ointment for topical application in healthy adult volunteers are:

- Frequency of treatment-emergent adverse events (TEAEs)
- The incidence rate of local skin responses (LSR, i.e., erythema, flaking/scaling, crusting, swelling, vesiculation/pustulation, erosion/ulceration, hyperpigmentation, hypopigmentation, and scarring) [Time Frame: Days 1 and 21]
- Changes from baseline in blood parameters (including hematology, chemistry, and other inflammation parameters such as C-reactive protein [CRP] and erythrocyte sedimentation rate [ESR]) [Time Frame: Days 1 and 21]

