#### *Treatment Period*

After confirmation of the application site, the subjects applied exosome ointment along with Vesiderm liposome cream (TID per day). The study product was applied daily (Day 1 to 20) with a gap of 4 hours between each dose to an area of healthy skin (one palm size) on the forearm using 1 fingertip unit (FTU). The Vesiderm liposome cream was applied in the same area immediately after.

All through the treatment period, the subjects completed the daily Subject Diary to capture adverse events (AEs; skin-related and other), concomitant medications, and time of study product application.

Follow-up calls were made every 3 days (Days 3, 6, 9, 12, 15, and 18) to check on compliance to the investigational product's (IP), and if subjects had any adverse events or taken any concomitant medications during the period. Any AEs reported by the subject during the calls were to be referred to the investigator for appropriate review and follow-up.

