#### *Adverse events*

All through the treatment period, the subjects completed the Subject Diary to capture the frequency of TEAEs.

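### The local skin response (LSR) incidence rate is in effect prevalence at Day 21, so a reaction that clears before the end-of-study visit does not enter the LSR result

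*Combined protocol and SAP*

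**What the plan says.** All references are to the Combined protocol and SAP.

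- **Endpoint.** The Introduction lists three safety endpoints: TEAE frequency, LSR and blood parameters. The second is "The incidence rate of local skin responses". It names nine visible signs, and the list ends "hyperpigmentation, hypopigmentation, and scarring) [Time Frame: Days 1 and 21".
- **Skin assessments.** The application area is assessed and photographed before treatment starts on Day 1. It is assessed again at EOS, where the procedures include "visual assessment of the area of application, AEs, and concomitant medications used". EOS falls on Day 21 (+3 days). For subjects who leave early, "The assessments at this visit were also to be conducted in case of early termination or withdrawal of any subject".
- **Between the visits.** Under Treatment Period, "the subjects completed the daily Subject Diary to capture adverse events (AEs; skin-related and other), concomitant medications". Calls on Days 3, 6, 9, 12, 15 and 18 check compliance and ask "if subjects had any adverse events or taken any concomitant medications during the period". Adverse events reported on a call go to the investigator. No skin grading is described for the calls. The Adverse events section adds that "the subjects completed the Subject Diary to capture the frequency of TEAEs".
- **Other products.** Study Participants excludes current topical treatment, several systemic drugs within 30 days before first application, and current treatment known to affect skin. The lead-in is "Subjects were to be excluded from the study if there was evidence of any of the following at screening or check-in, as appropriate". The supplied text states no matching rule for the dosing period.
- **Analysis.** Statistical Analysis is descriptive, with 10 subjects, summary tables and subject listings.

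**The concern.** An incidence rate counts subjects who have the event at some time in a period. A single grading after baseline counts subjects who have the sign on that day. The two agree only if no reaction clears before the visit. Irritation from a topical product can come and go within a 20-day course. Redness on Day 8 that has gone by Day 21 gives a correct grade of zero at EOS, and nothing in the plan brings the Day 8 finding into the LSR result.

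This is a first-in-human study meant to inform later ones, and LSR is the endpoint that looks specifically at the application site. A table headed incidence with no events could be taken to mean that no local reactions occurred during dosing, when it shows only that none was present at the end.

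**Working it through.** The plan has no figure of its own to reproduce: the sample size is a feasibility choice and no LSR rate is assumed. The check uses the schedule and simple counting.

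**Schedule for a completer**

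1. Planned applications (Dosage; Treatment Period): 3 per day × 20 days = 60.
2. Full days between the Day 1 assessment and EOS: Days 2 to 20 = 19 if EOS is on Day 21; Days 2 to 23 = 22 if EOS is on Day 24.
3. From the last dosing day (Day 20) to the grading: 21 − 20 = 1 day, up to 24 − 20 = 4 days.
4. Scheduled skin gradings after baseline: 1.

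**Effect on the count**

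Let k be the number of the 10 subjects with any LSR sign at the application area at any time from first application up to and including EOS. Let m be the number of those who are clear at the EOS grading. Assume that all 10 complete.

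- Any-time incidence = k/10.
- Result as the endpoint is timed = (k − m)/10.
- Shortfall = m/10, which is 10 percentage points for each missed subject.

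The documents give neither k nor m, so the shortfall cannot be estimated from them.

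**Illustration only.** Assume a true any-time incidence p, a share f of reacting subjects who are clear at EOS, and independent subjects. The chance that the Day 21 table shows at least one LSR is 1 − (1 − p(1 − f))^10.

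| p (assumed) | f = 0 | f = 0.5 | f = 0.75 |
|---|---|---|---|
| 10% | 0.65 | 0.40 | 0.22 |
| 20% | 0.89 | 0.65 | 0.40 |
| 30% | 0.97 | 0.80 | 0.54 |

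For example, with p = 20% and f = 0.5: 1 − (1 − 0.10)^10 = 0.65. The table shows the direction of the effect and does not estimate its size in this trial.

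**Which sections feed which endpoint**

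- A reaction present at EOS can enter the LSR result.
- A reaction that has cleared by EOS can enter the diary, a call record, the investigator's follow-up of a reported event, and the adverse event record at EOS. All of these feed the TEAE endpoint. No section links them to the LSR result.
- The signs graded under Assessment of area of application are redness, swelling, oozing/crusting, scratch marks, skin thickening and dryness. They do not match the nine LSR signs one for one. Vesiculation, erosion, pigment change and scarring have no graded item, and the text does not say how LSR incidence is derived from the grades. It is therefore not certain that even a lasting pigment change would be counted, although the EOS visual assessment and photograph could show it.

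**The case against.** The strongest reply is that nothing is lost. TEAE frequency is the first listed endpoint. Skin-related events are recorded daily, six calls ask about events and medication, reported events go to the investigator, and both are collected again at EOS. Early withdrawals have the EOS assessments. With 10 subjects and full listings, a reader can match a skin event to a zero LSR grade. The Days 1 and 21 time frame is also stated openly. All of this stands, and it is why the point is minor. It does not remove the mismatch between the label and the measurement, because LSR is reported as its own endpoint and nothing connects it to the adverse event records.

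Three stronger readings are tempting, and the documents do not support them.

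- *Reactions go unrecorded.* The capture routes just listed say otherwise.
- *The entry-only product exclusions cause the problem and bias LSR downward.* The single grading is the cause, since a reaction that clears untreated is missed in the same way. The direction is not established either: a non-study product could soothe the test area or irritate it.
- *Subjects were free to use any product during dosing.* The supplied text contains no restriction. However, it is a past-tense account that refers to a separately approved clinical protocol, so this silence does not show that no restriction existed.

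**Conclusion.** The point holds as a mismatch between the name of the LSR endpoint and what its schedule can measure. For completers the LSR result is prevalence 1 to 4 days after the last dosing day. It can fall below any-time incidence by 10 percentage points for each subject whose reaction has cleared, and no further size can be derived. This assumes that the LSR result is built from the scheduled assessments alone, as the stated time frame implies, and that no unscheduled examination is added to it. The effect is on how one of three endpoints reads in a 10-subject descriptive study. Severity is minor.

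**What to change.** 1. Label the existing result *LSR present at Day 21*, with a note that the visit may fall up to Day 24 and that early withdrawals are assessed at withdrawal.
2. Add one row, *Any LSR sign from first application to EOS*. It counts subjects with any of the nine listed signs at the application area, recorded by diary, call or investigator, whether treated or not. List concomitant topical or anti-inflammatory use beside it.
3. Record the sign, and whether it lies on the application area, with each skin-related adverse event. The current text does not say that these are captured.
4. Optionally, add one sentence asking subjects not to use non-study products electively on the test area from Day 1 to EOS, with treatment that the investigator judges necessary allowed and recorded. This protects the Day 21 grade from shifts either way. It does not address untreated clearing or investigator-directed treatment; the added row covers both.

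The cost is one table row, one medication column and two data fields, with no new visit. The downside is that some counted events will be self-reported and not graded by the dermatologist, so the row must say so, and the reported count may be higher. If dosing is already complete, the row can use only what the diaries and adverse event records hold; items 3 and 4 then apply to the next protocol.

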#### Dosage

MSC exosome ointment (70 µg MSC exosomes/g ointment) was the study intervention to be administered. It was administered as a topical intervention of one FTU per one hand area on the forearm (average hand area was 160-200 cm^2), thrice a day for 20 days.

#### Safety Assessment

Safety assessment included vital signs, clinical safety laboratory tests, inflammatory blood examinations, assessment of area of application and incidence and severity of AEs.

##### *Vital signs*

Vital signs including blood pressure (both systolic and diastolic), heart rate, respiratory rate, and body temperature were assessed on Day 1 (pre-treatment) and Day 21 (+3 days)

##### *Clinical safety laboratory tests*

Clinical safety laboratory tests including hematology panel, renal panel, and liver function test were assessed on Day 1 (pre-treatment) and Day 21 (+3 days)

##### *Inflammatory blood examinations*

Inflammatory blood examinations including CRP and ESR were performed on Day 1 (pre-treatment) and Day 21 (+3 days).

##### *Assessment of area of application*

The area of application was assessed by a dermatologist for parameters adapted from the SCORAD scale as shown in the next paragraph. The patient graded the subjective symptoms including itch and sleeplessness using an SCORAD scale.

This scale assessed the following:

- Intensity of reaction: The identified area of application was assessed for the intensity of signs including redness, swelling, oozing/crusting, scratch marks, skin thickening, and dryness and graded as none (0), mild (1), moderate (2) or severe (3).

- Subjective symptoms: The identified area of application was assessed for the subjective symptoms including itch and sleeplessness and graded from 0 (no itch or no sleeplessness) to 10 (worst imaginable itch or sleeplessness).

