### *Identification, visual assessment, and photography of application area*

A trained expert evaluator (an Investigator or designee) identified the area of study product application and performed visual assessments which were carried out using an adapted version of SCORing Atopic Dermatitis (SCORAD) scale and visual assessment score (VAS). A photograph of the area of application was also taken using a dedicated compact digital camera at the clinic where subject visits were done.

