#### Statistical Analysis

The analysis was conducted on all subject data at the time the study ended. Data collected in this study were presented using summary tables and subject data listings. Continuous variables were summarized using descriptive statistics, including the number of subjects (n), mean, median, standard deviation (SD), and minimum and maximum values. Categorical variables were summarized as frequencies and percentages. No formal statistical assessment, in terms of sample size, was conducted. A sample size of 10 subjects was considered a feasible sample size to provide sufficient safety data for a topical formulation study.

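### Skin thickening, and on narrower readings scratch marks and dryness, are graded as reactions but fall outside the closed list that defines the local skin response endpoint

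*Combined protocol and SAP*

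**What the plan says.** The Introduction lists the safety and tolerability endpoints. One is "The incidence rate of local skin responses", timed at Days 1 and 21, and its content is fixed in the same bullet: "LSR, i.e., erythema, flaking/scaling, crusting, swelling, vesiculation/pustulation, erosion/ulceration, hyperpigmentation, hypopigmentation, and scarring". The list is introduced by *i.e.*, which restates a definition; it does not offer examples.

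The grading is described elsewhere. Assessment of area of application states that "The area of application was assessed by a dermatologist for parameters adapted from the SCORAD scale" and then sets out what was graded. The first component begins "Intensity of reaction: The identified area of application was assessed for the intensity of signs" and names six signs on a four-point scale: "signs including redness, swelling, oozing/crusting, scratch marks, skin thickening, and dryness and graded as none (0), mild (1), moderate (2) or severe (3". Itch and sleeplessness are scored separately by the subject.

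The section on identification, visual assessment and photography names the tools as "an adapted version of SCORing Atopic Dermatitis (SCORAD) scale and visual assessment score (VAS"). It does not describe the content of the visual assessment score.

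Statistical Analysis says only that "Categorical variables were summarized as frequencies and percentages", with summary tables and listings. No section maps a graded sign to an LSR term, or says what grade or change in grade counts as an LSR.

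**The concern.** The plan treats all six signs as expressions of reaction at the application site, yet the endpoint that counts local skin responses recognises only some of them. A subject whose skin was graded moderate or severe for thickening at the end of study, with no other finding, would have a documented reaction and no LSR.

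Scratch marks and thickening can both point to an itchy or irritated site, which a study of application three times a day for 20 days would want to count. The exclusion works in one direction: it can lower LSR incidence but never raise it. This is a first-in-human study of 10 subjects whose results are meant to inform later studies, so even one uncounted subject visibly changes the reported percentage.

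**Working it through.** The plan gives no figure to reproduce: the sample size is a feasibility choice with no statistical inputs. The check is an item-by-item comparison of the two lists, followed by exact intervals for scale.

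**Inputs**

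- Nine LSR terms: Introduction, endpoint list.
- Six graded signs, each 0 to 3: Assessment of area of application.
- n = 10, single arm: Study Design and Statistical Analysis.

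**Step 1. Match each graded sign to an LSR term**

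| Graded sign | Nearest LSR term | Match |
|---|---|---|
| Redness | Erythema | Yes |
| Swelling | Swelling | Yes |
| Oozing/crusting | Crusting | Yes |
| Dryness | Flaking/scaling | Only if the two are equated |
| Scratch marks | Erosion/ulceration | Only if recorded as erosion |
| Skin thickening | None | No |

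**Step 2. Count the unmatched signs under each reading**

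- Strict: scratch marks, skin thickening and dryness, 3/6 = 50%.
- Dryness equated with flaking/scaling: scratch marks and skin thickening, 2/6 = 33%.
- Scratch marks also recorded as erosion: skin thickening alone, 1/6 = 17%.

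No reading brings the count to zero. The word *including* before the six signs leaves the graded list open, but it does not widen the endpoint list. These percentages are shares of scale items; they are not shares of events and do not measure bias.

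**Step 3. What one uncounted subject does to the endpoint**

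Each subject contributes 1/10 = 10 percentage points. Exact (Clopper-Pearson) 95% limits for x events in n are: lower = 2.5% quantile of Beta(x, n − x + 1), taken as 0 when x = 0; upper = 97.5% quantile of Beta(x + 1, n − x). For x = 0 the upper limit reduces to 1 − 0.025^(1/10) = 0.3085.

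| Counted as LSR | Incidence | Exact 95% interval |
|---|---|---|
| 0/10 | 0% | 0 to 30.8% |
| 1/10 | 10% | 0.3 to 44.5% |
| 2/10 | 20% | 2.5 to 55.6% |

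The values x = 1 and x = 2 are illustrations. The document does not say how many subjects, if any, had only an unmatched sign.

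**The case against.** The strongest objection is that the document nowhere says LSR incidence is derived from the adapted SCORAD. A visual assessment score is named and left undescribed, and LSR could have been recorded on its own. This stands, so a reader who infers that SCORAD data were collected for the endpoint and then dropped goes further than the text. The mismatch remains all the same: a separate record kept to the nine terms would also exclude thickening.

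Second, such a reaction need not go unreported. The daily diary captures skin-related adverse events, the follow-up calls ask about them, and the end-of-study visit includes photography and adverse event review. With 10 subjects, a listing of grades would show every sign. This also stands and confines the defect to LSR incidence. A reader might infer that the trial's overall finding is tilted towards good tolerability. The document does not support that: LSR is one of several safety endpoints, and nothing makes it the headline result. Against this, no section says that a dermatologist's grade triggers an adverse event report, so the other routes do not guarantee the count.

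Third, the scenario needs thickening or scratch marks without redness, swelling, crusting or any other listed response. The document gives no rate for that. Any probability that at least one of 10 subjects is missed would rest on an assumed rate, so none is relied on here.

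Fourth, the reverse gap is larger: 6, 5 or 4 of the nine LSR terms, under the three readings in order, have no named graded sign. That is correct and comes from the same unreconciled lists. Adding graded items for those terms would still leave skin thickening outside the endpoint, so both directions need attention.

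**Conclusion.** The concern holds in a limited form. The LSR endpoint, as worded, excludes skin thickening on any reading, scratch marks unless they are recorded as erosion, and dryness unless it is equated with flaking/scaling. A subject with only such a sign, at any grade up to severe, is not counted. The effect is 10 percentage points of LSR incidence per subject, always downward.

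This rests on two assumptions: that *i.e.* closes the list, which is its ordinary meaning, and that all 10 subjects are in the denominator. The frequency of affected subjects cannot be determined from the document, and neither can any actual distortion of the results. The point is worth acting on because correction needs no new data.

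**What to change.** Reconcile the endpoint list in the Introduction with the signs in Assessment of area of application:

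- State the mapping in writing, including whether dryness is the same as flaking/scaling and how scratch marks are classified.
- Make every graded sign count towards LSR incidence when its end-of-study grade exceeds the subject's own Day 1 grade. The comparison fits the endpoint's Day 1 and Day 21 time frame and keeps pre-existing dryness from counting as a response.
- Report incidence per sign and for any sign.

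The document is written in the past tense. If the data have been analysed, leave the nine-term result as it is and present the wider count beside it as a labelled supplementary tabulation, so that it is not taken for the endpoint as originally defined.

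The cost is a short change to the definition and one extra table; no new assessments are needed. There are two small downsides. Incidence can only stay the same or rise. With no control arm, some incidental scratch marks or dryness may also be counted, but the per-sign table lets the reader see which signs drive the total.
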